15.3.2. MISSING DATA METHODS FOR EXPLORATORY EFFICACY VARIABLE(S)

No imputation will be applied.

15.3.3. ANALYSIS OF EXPLORATORY EFFICACY VARIABLES

Dyspnea score and the change in dyspnea score will be summarized at each timepoint of interest on Day 7 (pre-dose and 30 minutes, 1, 1.5, 2, 4, 8, 11 and 12 hours post-dose). Treatment comparisons of change from baseline will be performed using an ANCOVA adjusting for treatment, treatment period and patient, and using pre-dose Day 1 baseline value as a covariate, like the hypothesis described in [section 15.1.3](#). The model will be additive; therefore no log-transformation will be applied.

Document: Z:\RPL554\AZA40375\Biostatistics\Documentation\SAP\Verona RPL554-DP-201 SAP v2.0 – Part B

Author: [name] / [name]

Version Number: 2.0

Version Date: [08JUL2019]

Template No.: CS_TP_BS016 Revision 5

Reference: CS_WI_BS005

Effective Date: 01Apr2018

Copyright © 2009, 2010, 2012, 2016, 2018 IQVIA. All rights reserved. The contents of this document are confidential and proprietary to IQVIA Holdings Inc. and its subsidiaries. Unauthorized use, disclosure or reproduction is strictly prohibited.

16. SAFETY OUTCOMES

All outputs for safety outcomes will be based on the SAF.

There will be no statistical comparisons between the treatment groups for safety data, unless otherwise specified with the relevant section.

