Duration of Treatment:	
Part A: 1 to 2 week screening period, followed by single dose treatment and then an analysis period (exact timing to be determined).
 
Part B: Five treatment periods, each consisting of 7 days treatment, separated by 7 to 10 day washout periods.

Statistical Methods:	Treatments will be compared using appropriate analysis of covariance models for Parts A and B, respectively. Multiplicative models will be used for FEV ₁ and additive models for blood pressure, pulse rate and ECG heart rate. RPL554 by DPI treatments will be compared to placebo using a closed test procedure starting with the highest dose of RPL554.
Sample Size Determination:	The sample size is determined for Part B. Assuming a residual coefficient of variation (CV) of 6% for peak FEV ₁ , 30 patients will give an 80% power to detect a pairwise difference in peak FEV ₁ of 4.6%. Assuming a mean baseline FEV ₁ of 1.5 L, this will correspond to a difference of about 70 mL. To account for withdrawals, approximately 36 patients will be randomized to Part A.

TABLE OF CONTENTS AND LIST OF TABLES AND FIGURES

Table of Contents

SPONSOR SIGNATURE PAGE	2
INVESTIGATOR SIGNATURE PAGE	3
CONFIDENTIALITY STATEMENT	3
CONTACT LIST	4
DETAIL OF AMENDMENTS SINCE THE PREVIOUS VERSION	5
SYNOPSIS	6
TABLE OF CONTENTS AND LIST OF TABLES AND FIGURES	10
Table of Contents	10
List of Tables and Figures	13
LIST OF ABBREVIATIONS	14
1 INTRODUCTION	15
1.1 Disease and Study Medication Review	15
1.2 Summary of Risks and Benefits	17
2 OBJECTIVES	18
2.1 Part A	18
2.1.1 Primary Objective	18
2.1.2 Secondary Objectives	18
2.2 Part B	18
2.2.1 Primary Objective	18
2.2.2 Secondary Objectives	18
2.2.3 Exploratory Objectives	18
3 INVESTIGATIONAL PLAN	19
3.1 Overall Study Design and Plan Description	19
3.2 Discussion of Study Design, including the Choice of Control Groups	19
3.3 Planned Duration of the Study	20
3.4 Definition of the End of the Study	20
4 SELECTION OF STUDY POPULATION	21
4.1 Inclusion Criteria	21
4.2 Exclusion Criteria	22
4.3 Removal of Patients from Therapy or Assessment	23
4.3.1 Study Treatment Discontinuation	23
4.3.2 Patient Withdrawal	23
4.3.3 Study Discontinuation	24
4.3.4 Replacement Policy	24
5 STUDY TREATMENTS	25

5.1	Study Treatments Administered.....	25
5.1.1	Treatments Administered in Part A	25
5.1.2	Treatments Administered in Part B	25
5.2	Identity, Preparation and Labeling of Study Treatments	26
5.3	Selection of Doses and Dosing Schedule.....	26

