1.2 Summary of Risks and Benefits

Data from non-clinical studies had suggested a potential for hypotension and tachycardia. However, in the clinical studies to date, RPL554 has been well tolerated in healthy subjects as well as patients with moderate to severe COPD, asthma and allergic rhinitis. The most common adverse events that have been reported at least twice in subjects who have received single or multiple doses of the nebulized suspension of RPL554 were generally mild and in descending order of frequency were headache, cough, dizziness, and palpitations. Adverse events for single and multiple dose studies are summarized in the Investigator's Brochure.

The suspension formulation of RPL554 has favorable non-clinical toxicology and pharmacokinetic data.

While there have been few adverse events related to the cardiovascular or gastrointestinal systems, small and transient increases in heart rate at doses of 6 and 12 mg have been reported. Holter assessments have indicated no arrhythmogenic potential in the completed studies.

In single dose studies, there appears to be an increase in the rate of headache that is most pronounced at doses over 6 mg. Results from multiple dose data in patients with COPD suggests a transient increase in dizziness, the majority of which occurred during spirometry maneuvers or dosing; otherwise, the rate of adverse events was similar between RPL554 and placebo treated patients.

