9.4.7 Safety

Safety data including laboratory safety tests, 12-lead ECG, vital signs and physical examinations, will be summarized by treatment group and timepoint of collection, when appropriate, for each of the two parts separately. For continuous variables, the change from baseline (pre-dose at each treatment period) to each post-dose time point will also be calculated and summarized. Data will further be illustrated by shift tables (showing changes from low/normal/high) and shift plots for selected time points. Separate listings will be generated of abnormal values occurring after the first dose of study treatment.

In Part A, change from baseline in peak pulse and peak heart rate will be compared between the treatments using analysis of covariance models with fixed factor treatment, and using the pre-dose baseline value as a covariate. In Part B, change from baseline in peak pulse will be compared between the treatments using analysis of covariance models with fixed factors for treatment, period and patient, and using the pre-dose Day 1 baseline value as a covariate. Additive model will be used for pulse and heart rate.

Coded adverse event terms will be presented by system organ class (SOC) and preferred term and summarized by treatment group for each part. Summary tables by treatment group with total number and number of patients with adverse events, SAEs, adverse events leading to discontinuation of study treatment, causally related adverse events and severe adverse events will be produced. Further SAEs, causally related adverse events and adverse events of each intensity will be summarized by SOC and preferred term.

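### The synopsis commits to additive ANCOVA comparisons of blood pressure, but section 9.4.7 and both SAPs plan none, so Part B will report blood pressure by treatment without a dose-minus-placebo difference or confidence interval

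*SAP*

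**What the plan says.** **Protocol synopsis, Statistical Methods.** "Treatments will be compared using appropriate analysis of covariance models for Parts A and B, respectively". FEV₁ gets multiplicative models. The other variables get "additive models for blood pressure, pulse rate and ECG heart rate", with blood pressure listed first.

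**Protocol 9.4.7.** The modelled comparisons are peak pulse and peak heart rate in Part A. For Part B: "In Part B, change from baseline in peak pulse will be compared between the treatments using analysis of covariance models". The section ends its modelling text with "Additive model will be used for pulse and heart rate" and does not mention a blood pressure model. It does plan description: "Safety data including laboratory safety tests, 12-lead ECG, vital signs and physical examinations, will be summarized by treatment group and timepoint of collection", and for continuous variables "the change from baseline (pre-dose at each treatment period) to each post-dose time point will also be calculated and summarized".

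**SAP Part A and SAP Part B, section 16.** Both carry the same rule: "There will be no statistical comparisons between the treatment groups for safety data, unless otherwise specified with the relevant section". The exceptions are peak heart rate (Part A 16.3), peak pulse (Part A 16.4) and peak pulse (Part B 16.4). Neither SAP makes an exception for blood pressure.

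**Section 3.3 of each SAP.** Part A answers that changes from protocol are not applicable; Part B answers that there are none.

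**Protocol 1.2.** "Data from non-clinical studies had suggested a potential for hypotension and tachycardia". The next sentence reports that the drug has been well tolerated in clinical studies to date.

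**The concern.** The protocol makes one statement about blood pressure in its synopsis and a narrower one in its methods section. The SAPs follow the narrower one without recording a difference. Protocol 9.1 requires departures from the planned analysis to be detailed and justified in the study report, and an undeclared one is easily missed.

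Of the two non-clinical signals in section 1.2, tachycardia gets a between-treatment comparison and hypotension does not. Part B is where this matters most: each patient is to receive placebo and all four doses, so the within-patient contrast is the most precise blood pressure evidence the trial can give. Without it, the reader of the study report gets means by treatment and counts of extreme values, and has to judge unaided whether a difference between doses and placebo exceeds noise.

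**Working it through.** **1. The passages side by side**

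| Source | Blood pressure | Pulse | Heart rate |
|---|---|---|---|
| Synopsis (Parts A and B) | additive model | additive model | additive model |
| Protocol 9.4.7, Part A | descriptive | additive ANCOVA | additive ANCOVA |
| Protocol 9.4.7, Part B | descriptive | additive ANCOVA | descriptive |
| SAP Part A 16.3, 16.4 | descriptive | tested as in 15.2.3 | tested as in 15.2.3 |
| SAP Part B 16.3, 16.4 | descriptive | additive ANCOVA | descriptive |

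Planned model-based blood pressure comparisons: none in 9.4.7, none in SAP Part A, none in SAP Part B.

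**2. What is described**

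- SAP Part A 16.4 lists actual values, change from baseline at each post-dose time, and incidence of markedly abnormal values.
- SAP Part B 16.4 lists actual values and incidence of markedly abnormal values. Change from baseline is not listed for blood pressure, although 9.4.7 requires it.
- The systolic change criterion for a markedly abnormal value is at least 20 mmHg in Part A and at least 40 mmHg in Part B. The diastolic change criterion is at least 20 mmHg in both.

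**3. The plan's own design figure**

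The only computed figure concerns peak FEV₁ (protocol 9.5), and it reproduces.

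- Log-scale SD = √ln(1 + 0.06²) = 0.0599.
- SE = 0.0599 × √(2/30) = 0.0155.
- ln(1.046)/SE = 0.0450/0.0155 = 2.91.
- With a paired t on 29 df, power is 80.2%.

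This point does not depend on that figure; it only confirms 30 patients as the basis for a Part B contrast.

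**4. Precision of a blood pressure contrast in Part B**

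Inputs: 30 completing patients (protocol 4.3.4 and 9.5), five periods, and an assumed within-patient residual SD of 7 to 11 mmHg. The documents give no SD.

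- Residual df, counting patient as a fixed term: 150 − 1 − 29 (patients) − 4 (treatments) − 4 (periods) − 1 (baseline) = 111. So t(0.975) = 1.98.
- Half-width of the 95% CI = t × SD × √(2/30) = 1.98 × SD × 0.258.
- SD 7: 3.6 mmHg. SD 9: 4.6 mmHg. SD 11: 5.6 mmHg.

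**5. The same contrast in Part A**

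Six patients per arm, df = 36 − 6 − 1 = 29, t(0.975) = 2.05, assumed between-patient SD 8 to 15 mmHg.

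- Half-width = 2.05 × SD × √(2/6) = 9.4 mmHg (SD 8) to 17.7 mmHg (SD 15).

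**6. What the counts can show**

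Take SD 9 per reading, so the SD of a change between two readings is 9 × √2 = 12.7 mmHg, with normal errors and a true mean systolic fall of 5 mmHg.

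- Fall of at least 40 mmHg, one reading: z moves from 40/12.7 = 3.14 to 35/12.7 = 2.75, and the probability from 0.08% to 0.30%. In 30 patients that is 0.03 to 0.09 expected.
- The same criterion, lowest of the ten post-dose readings on Days 1 and 7 (independent, one shared baseline): about 0.2 to 0.7 patients in 30.
- Fall of at least 20 mmHg, one reading: z moves from 1.57 to 1.18, and the probability from 5.8% to 11.9%. In 30 patients that is 1.7 to 3.6 expected.

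Part B's systolic change criterion would barely register a 5 mmHg mean shift. A criterion of 20 mmHg would register more of it, but still as a difference of about two patients per reading.

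**The case against.** The strongest reply is that the synopsis is the outlier. The Part A secondary objective names effects on peak pulse and heart rate. The separately listed change-from-baseline safety endpoints are peak pulse and peak heart rate in Part A (9.3.1.2) and peak pulse in Part B (9.3.2.2). Blood pressure appears there only under general supine vital signs. Section 9.4.7 and both SAPs agree with one another on blood pressure. Modelling pulse and heart rate also fits the clinical record in section 1.2, which reports small transient heart-rate increases and otherwise good tolerability. On this reading the synopsis wording is a leftover, and deleting it resolves the contradiction. That is plausible and stands as an alternative remedy, but the deletion then has to be made and recorded, and neither SAP records it.

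Several stronger readings are tempting and are not supported:

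- A reader might infer that blood pressure gets no estimate by dose at all. Values by treatment and time point are planned in both parts, so a moderate dose-related fall could be seen in the means. What is missing is the difference from placebo with its confidence interval.
- A reader might infer that hypotension is an established risk of the drug class. Section 1.2 reports only a potential suggested by non-clinical data.
- A reader might infer from step 6 that Part B's outlier table is blind to falls in pressure. The 40 mmHg systolic criterion is its least sensitive line. The table also counts systolic values of 90 mmHg or below, diastolic values of 50 mmHg or below, and diastolic falls of at least 20 mmHg.
- A reader might want the same model added to Part A. Part A was locked, unblinded and analysed before Part B, so the model would be post hoc there, and with six patients per arm it would be imprecise (step 5). SAP Part A also has no additive model ready to reuse: it refers peak pulse and peak heart rate to 15.2.3, a log-ratio model, without saying that the model becomes additive as 9.4.7 requires.

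**Conclusion.** The inconsistency is real and undeclared: the synopsis states a blood pressure comparison that neither 9.4.7 nor either SAP contains. Separately, SAP Part B 16.4 falls short of 9.4.7 by omitting the blood pressure change-from-baseline summary. The two SAPs also differ in their systolic change criterion, 20 against 40 mmHg, so their counts are not comparable.

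The practical loss is confined to Part B. There the trial could estimate each dose-minus-placebo difference to within about ±3.6 to ±5.6 mmHg and plans no such estimate. That range rests on an assumed within-patient SD of 7 to 11 mmHg and 30 complete patients. A minimum over several readings may have a different SD.

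The primary endpoint and its test are unaffected. This is a gap in safety reporting that should be closed; it does not undermine the trial's efficacy conclusions.

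**What to change.** **Part B.** Amend SAP Part B 16.4 and align protocol 9.4.7 before Part B is unblinded; if that has already happened, label the analysis post hoc.

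- Add the change-from-baseline summary for supine systolic and diastolic pressure by treatment and time point.
- Apply the additive crossover ANCOVA already specified for peak pulse (treatment, period, patient and baseline) to change from Day 1 pre-dose in systolic and diastolic pressure, on Day 1 and Day 7. One suitable response is the minimum over the first 4 hours, which uses the scheduled 1, 2 and 4 hour readings. Report each dose's difference from placebo with a 95% CI and treat the p-values as nominal.
- State why the systolic change criterion differs from Part A, or reconcile the two.

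**Part A.** Record in the study report that the blood pressure comparison stated in the synopsis was not planned in the SAP.

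**Alternative.** If the sponsor does not intend the Part B model, remove blood pressure from the synopsis sentence and disclose the change in SAP 3.3. The change-from-baseline summary is still owed under 9.4.7.

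**Cost.** The Part B change reuses a specified model on data already scheduled for collection and adds summary and model output. The downside is a few more nominal safety comparisons, which should be read as estimates with intervals rather than as tests.

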16.1. ADVERSE EVENTS

Adverse Events (AEs) will be coded by MedDRA dictionary using the version specified in the data management plan.

Treatment emergent adverse events (TEAEs) are defined as AEs that started or worsened in severity on or after the first dose of study medication, based on the investigator assessment of severity. TEAEs will be assigned to treatment groups based on actual treatment received. TEAEs, like medications, may be assigned to multiple treatment groups due to the cross-over design of the study. This will depend on the occurrence date and duration of each TEAE.

See [Appendix 2](#) for handling of partial dates for AEs. In the case where it is not possible to define an AE as treatment emergent or not, the AE will be classified by the worst case; i.e. treatment emergent.

An overall summary of number of patients within each of the categories described in the sub-section below, will be provided as specified in the templates.

Listings will include TEAEs and Non-TEAEs.

16.1.1. ALL TEAES

Incidence of TEAEs will be presented by System Organ Class (SOC) and Preferred Term (PT) and broken down further by maximum severity and relationship to study medication.

16.1.1.1. Severity

Severity is classed as mild/ moderate/ severe (increasing severity). TEAEs starting after the first dose of study

Document: Z:\RPL554\AZA40375\Biostatistics\Documentation\SAP\Verona RPL554-DP-201 SAP v2.0 – Part B

Author: [name] / [name]

Version Number: 2.0

Version Date: [08JUL2019]

Template No.: CS_TP_BS016 Revision 5

Reference: CS WI RS005

Effective Date: 01Apr2018

Copyright © 2009, 2010, 2012, 2016, 2018 IQVIA. All rights reserved. The contents of this document are confidential and proprietary to IQVIA Holdings Inc. and its subsidiaries. Unauthorized use, disclosure or reproduction is strictly prohibited.

medication with a missing severity will be classified as severe. If a patient reports a TEAE more than once within that SOC/ PT, the AE with the worst-case severity will be used in the corresponding severity summaries.

16.1.1.2. Relationship to Study Medication

Relationship, as indicated by the Investigator, is classed as “yes” or “no”. A related TEAE is defined as a TEAE with a relationship to study medication as “yes”. TEAEs with a missing relationship to study medication will be regarded as relationship = “yes” to study medication. If a patient reports the same AE more than once within that SOC/ PT, the AE with the worst-case relationship to study medication will be used in the corresponding relationship summaries.

16.1.2. TAEs LEADING TO DISCONTINUATION FROM STUDY MEDICATION

TEAEs leading to discontinuation from the study will be identified by using the question "Did the AE cause the Patient to discontinue from the study?" from the AE page of the eCRF.

For TEAEs leading to discontinuation from the study medication, summaries of incidence rates (frequencies and percentages) by SOC and PT will be prepared.

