4.3 Removal of Patients from Therapy or Assessment

4.3.1 Study Treatment Discontinuation

Study treatment must be discontinued for the following reasons:

- Unacceptable toxicity related to study treatment
- Intolerable or persistent adverse events of any severity
- General or specific changes in the patient's condition rendering the patient unacceptable for further treatment in the judgment of the Investigator
- Clinically significant progression of disease
- Pregnancy in a female patient

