7.4.1.2.3 Causality

The Investigator will assess causal relationship between the study medication and each adverse event, and answer "yes" or "no" to the question, "Do you consider that there is a reasonable possibility that the event may have been caused by the study medication?"

For SAEs, causal relationship will also be assessed for study procedures, additional study medication, and other medication. Note that for SAEs that could be associated with any study procedure, the causal relationship is implied as "yes".

A guide to the interpretation of the causality question is found in Section [14.2](#).

7.4.1.2.4 *Action and Outcome*

- Action taken with study medication (none, study medication stopped, study medication temporarily interrupted)
- Other actions (none, concomitant medication, study discontinuation, hospitalization, other)
- The outcome and date of outcome according to the following definitions:
 - Recovered or resolved (adverse event disappeared)
 - Recovering or resolving (patient is recovering)
 - Not recovered or not resolved (adverse event remains without signs of improvement)
 - Recovered or resolved with sequelae (adverse event has resulted in permanent disability or incapacity)
 - Fatal
 - Unknown (only applicable if patient has been lost to follow-up)
- Seriousness (yes or no)

7.4.1.3 *Reporting Procedure for SAEs*

The Investigator must report all SAEs to the Sponsor as soon as practical, but in all cases within 24 hours of awareness. Any fatal SAEs notified in the 28-day period after the last dose of study drug must also be reported.

SUSARs will be determined by the Sponsor's Medical Monitor.

SAEs will be reported to the IRB and regulatory authority(ies) according to local requirements.

All adverse events will be followed until they have abated, or until a stable situation has been reached. Depending on the event, follow up may require additional tests or medical procedures as indicated, and/or referral to the patient's general physician or a medical specialist.

It is the responsibility of the Investigator to ensure that any necessary additional therapeutic measures and follow-up procedures are performed.

7.4.2 *Pregnancy*

In addition to the Screening serum pregnancy test (see Section 7.1.4), urine pregnancy tests will also be performed by the study center on women of childbearing potential at Screening (confirmed to be negative prior to the chest X-ray) and during the study.

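### The Part B SAP titles a table as drug discontinuation due to TEAEs but fills it from a question about leaving the study, so rates by dose may be misstated

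*SAP*

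**What the plan says.** Protocol 9.4.7 asks for summaries by treatment group, for each part, that include "adverse events leading to discontinuation of study treatment".

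Protocol 7.4.1.2.4 has the investigator record two distinct items for an adverse event. The first is "Action taken with study medication (none, study medication stopped, study medication temporarily interrupted". The second is "Other actions (none, concomitant medication, study discontinuation, hospitalization, other". Stopping the drug belongs to the first item, and leaving the study belongs to the second.

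The protocol also has separate sections for the two decisions. Section 4.3.1 begins "Study treatment must be discontinued for the following reasons" and lists the reasons. Section 4.3.2 covers withdrawal of the patient.

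The heading of SAP Part B 16.1.2 refers to events "LEADING TO DISCONTINUATION FROM STUDY MEDICATION". The selection rule is "TEAEs leading to discontinuation from the study will be identified by using the question", and the question, from the AE page of the eCRF, is "Did the AE cause the Patient to discontinue from the study". The section closes with "For TEAEs leading to discontinuation from the study medication, summaries of incidence rates (frequencies and percentages) by SOC and PT will be prepared". It names no other field. SAP Part B 3.3 declares no change from the protocol.

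**The concern.** The heading and the closing sentence describe one event, and the selection rule identifies another. A programmer who follows the section would fill a table about the drug from a variable about study exit.

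In a single-dose part the distinction hardly matters. Part B, however, has five 7-day treatment periods separated by washouts, so stopping the drug within a period and leaving the study can in principle be different events. Safety and tolerability of repeat doses is a secondary objective of Part B, and this is the one summary by treatment group in which stopping the drug because of an event is meant to appear. If its source is wrong, the table does not meet Protocol 9.4.7, and the departure is undeclared.

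**Working it through.** The plan states no figure for this point, so there is none to reproduce. The check is a comparison of the texts, followed by the weight of one misclassified event.

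**Step 1. What each case would do under the rule as written.**

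| Case | Action taken with drug (7.4.1.2.4) | Answer to the study question | In the 16.1.2 table? | Consequence |
|---|---|---|---|---|
| Drug stopped for an event, patient leaves the study | stopped | yes | yes | agrees with 9.4.7 |
| Drug stopped for an event, patient stays in the study | stopped | no | no | missed |
| Dosing halted in one period, resumed in a later period | stopped or temporarily interrupted; the documents do not say which | no | no | not shown |
| Patient leaves for an event during a washout | no drug being taken | yes | yes | counted with no dose in use |

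The rule agrees with the protocol's table only in the first case. The second and third can understate the count for a dose. The fourth can overstate it.

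**Step 2. Comparison with the Part A SAP.** Section 16.1.2 there uses the same question, but its section heading and summary sentence both refer to the study, so label and source match. In Part B the label refers to the drug and the question is the same. This suggests an oversight but does not prove one.

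**Step 3. Weight of one event.** Protocol 4.3.4 plans 30 completers from about 36 randomized patients. SAP Part B 5.3 counts a patient under each treatment received. I assume nearly every patient receives every treatment, so a column has n of about 30 to 36.

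- One event: 1/36 = 2.8%; 1/30 = 3.3%.
- Two events: 2/36 = 5.6%; 2/30 = 6.7%.

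**Step 4. Chance that a column misses at least one event.** The documents give no rate for drug stops without study withdrawal. Let q be an assumed rate per patient-period, with patients independent. The chance is 1 − (1 − q)^n.

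| Assumed q | n = 30 | n = 36 |
|---|---|---|
| 0% | 0% | 0% |
| 1% | 26% | 30% |
| 3% | 60% | 67% |
| 5% | 79% | 84% |

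These values show sensitivity only and do not predict what will happen.

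**Step 5. Room for over-counting.** Protocol 6.4.2.3 brings patients back 7 to 10 days after Day 7, which leaves 6 to 9 dose-free days in each of four gaps, or 24 to 36 days. Dosing covers 5 × 7 = 35 days. The dose-free share from Period 1 to the end of Period 5 is 24/59 = 41% to 36/71 = 51%. This is the time in which the fourth case could arise. It does not show how often it would.

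**The case against.** The strongest reply is that the harm has not been shown to occur. Protocol 4.3.1 does not say whether a patient who stops the drug leaves the study or may enter the next period. Some of its reasons read as lasting, and the visit procedures in 6.4 and 6.5 describe no skipped period or off-drug follow-up. If every drug stop for an event also ended participation, no drug stop would be missed. This stands, and it is why the point is worded conditionally. A reader might infer that drug stops are being lost and that tolerability by dose is overstated. The documents do not support that: they neither allow nor exclude the case on which it depends, and the same rule can also over-count.

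Second, other outputs limit the damage. SAP Part B 13 presents exposure in days by treatment, section 9 the number discontinued in each period, and Appendix 1 calls for listing all CRF variables that have data. The other TEAE summaries are unaffected. This also stands, but none of these outputs replaces the required table. Exposure does not show why dosing ended, capsule totals are presented by sequence, and a listing is not a rate by dose.

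Third, selecting only on drug stopped might miss a patient who halts dosing in one period and resumes in another, because the site could record an interruption. This is correct, and the fix allows for it.

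Fourth, this may be only a label slip, and the output templates and eCRF that might settle it are not available for review. That is possible. The SAP text would still need correcting, because the only rule it states does not produce the table that Protocol 9.4.7 requires.

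**Conclusion.** The point holds in a limited form. The title and summary of SAP Part B 16.1.2 do not match its source field, the section does not deliver the table in Protocol 9.4.7, and SAP 3.3 does not declare the departure. This rests on the text alone.

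The effect on results is conditional. The rate by dose may be misstated in either direction, with understatement possible. Each misclassified event is worth about 2.8 to 3.3 percentage points of a column, assuming 30 to 36 patients per treatment. Two missed events at one dose would show 0% in place of 5.6 to 6.7%, but that is a hypothetical case. How many events are affected cannot be derived from the documents, and the number may be zero. The rule also applies to placebo, so a consistent bias in favour of the drug cannot be claimed. The error is confined to one safety summary and should be corrected because the correction is cheap.

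**What to change.** In SAP Part B 16.1.2:

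- Select these TEAEs by the action-taken item with the category *study medication stopped*, and assign each to the treatment being taken at that time.
- Show *temporarily interrupted* on a separate line, so that a stop within one period followed by dosing in a later period is not lost.
- Keep the existing eCRF question for a separate line titled as study discontinuation.

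In the protocol, sections 4.3.1 and 4.3.2 should be reconciled on whether stopping treatment in one period entails withdrawal from the study. Which answer is right is not a matter for this review.

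The SAP change costs about one sentence and one or two extra rows or a small table. It needs no new data if the eCRF carries the action-taken item that Protocol 7.4.1.2.4 already requires. The protocol change is a clarification of wording.
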